Hematology including Reticulocyte Count and Coagulation panel.	X	X		X		X	X		X	X	X	See Appendix 2 . See Section 8.2.8 for guidance on abnormal lab results	
Lipid panel			X							X		8-hour fast required	
CCI [REDACTED]	[REDACTED]	[REDACTED]	[REDACTED]	[REDACTED]	[REDACTED]	[REDACTED]	[REDACTED]	[REDACTED]	[REDACTED]	[REDACTED]	[REDACTED]	[REDACTED]	
Blood collection for biomarker evaluation – Serum proteomics		X				X	X			X		See Section 8.8	
CCI [REDACTED]		[REDACTED]				[REDACTED]	[REDACTED]		[REDACTED]			See Section 8.8	

	Screening	Intervention Period											Follow-up	Notes
Visit Identifier	Day -28	Day 1 Week 0 Base line	Day 2 Week 0	Day 4 Week 0	Day 8 Week 1 (by Phone)	Day 15 Week 2	Day 29 Week 4	Day 4 3 Week 6 (by Phone)	Day 5 7 Week 8	Day 85 Week 12 (EOT/ET)	Day 113 Week 16 (EOS)			
	Visit 1	Visit 2	Visit 3	Visit 4	Visit 5	Visit 6	Visit 7	Visit 8	Visit 9	Visit 10	Visit 11			
CCI [REDACTED]		[REDACTED]		[REDACTED]		[REDACTED]	[REDACTED]		[REDACTED]	[REDACTED]	[REDACTED]		See Section 8.1.8	
CCI [REDACTED]							[REDACTED]			[REDACTED]		[REDACTED]	ee Section 8.5	
Lymphocyte subsets		X		X		X			X	X	X		See Appendix 2	
Urinalysis	X	X				X	X		X	X	X		See Appendix 2	
Serum pregnancy test	X												Required for all WOCBP	
Urine Pregnancy Test (conducted at study site)		X				X	X		X	X	X			

	Screening	Intervention Period											Follow-up	Notes
Visit Identifier	Day -28	Day 1 Week 0 Base line	Day 2 Week 0	Day 4 Week 0	Day 8 Week 1 (by Phone)	Day 15 Week 2	Day 29 Week 4	Day 43 Week 6 (by Phone)	Day 57 Week 8	Day 85 Week 12 (EOT/ET)	Day 113 Week 16 (EOS)	Visit 11 is 4 weeks after last dose in case of early study termination.		
	Visit 1	Visit 2	Visit 3	Visit 4	Visit 5	Visit 6	Visit 7	Visit 8	Visit 9	Visit 10	Visit 11			
Banked Biospecimen Sample (Prep D1)		X										See Section 8.7.2 If not collected on the designated collection day, collect at the next available time point when biospecimens are being collected in conjunction with a participant visit.		
Banked Biospecimen Sample (Prep B1.5)		X									X	See Section 8.8.2		
Banked Biospecimen Sample (Prep B2.5)		X									X	See Section 8.8.2		
Blood samples collection for viral studies		X										Only analyzed on suspected viral infection/reactivation. See Section 8.2.8.2		
HIV testing	X											See Appendix 2		

	Screening	Intervention Period										Follow-up	Notes

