5.3.1. Meals and Dietary Restrictions

On study visit days (Day 1 and Week 12), participants must comply with fasting requirements for at least 8 hours prior to the visit. Water and permitted non-study medications are allowed ([Section 8.2.8](#)).

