8. STUDY ASSESSMENTS AND PROCEDURES

- Study procedures and their timing are summarized in the [Schedule of Activities](#). Protocol waivers or exemptions are not allowed.
- Immediate safety concerns should be discussed with the sponsor immediately upon occurrence or awareness to determine if the participant should continue or discontinue study intervention.
- Adherence to the study design requirements, including those specified in the [Schedule of Activities](#), is essential and required for study conduct.
- All screening evaluations must be completed and reviewed to confirm that potential participants meet all eligibility criteria. The investigator will maintain a screening log to record details of all participants screened and to confirm eligibility or record reasons for screening failure, as applicable. Participants will be screened (Visit 1) within 28 days prior to administration of the study intervention to confirm that they meet the participant selection criteria for the study. The investigator (or an appropriate delegate at the investigator site) will obtain informed consent from each participant, in accordance with the procedures described in [Section 10.1.3](#).
- Procedures conducted as part of the participant's routine clinical management (eg, blood count) and obtained before signing of the ICF may be utilized for screening or baseline purposes provided the procedures met the protocol-specified criteria and were performed within the time frame defined in the [Schedule of Activities](#).
- Screening laboratory tests with abnormal results may be repeated once to confirm abnormal results; the last value will be used to determine eligibility. If results return to normal within the 4-week screening period, the participant may enter the study.
- Due to possible need for PPD testing and chest radiograph, screening procedures may be performed over more than 1 visit in the 28 days prior to the Day 1 visit.
- Visit windows are based on Day 1 visit. To assure consistency and reduce variability, all study visits should occur in the morning whenever possible. On days of study visits, participants will receive their dose at the clinic during the visit.
- Participants are required to fast for at least 8 hours prior to all visits that include lipid profile panel testing (Day 1 and Week 12). During the fasting period, participants should refrain from all food and liquids (water and permitted non-study medications are allowed).

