8.2.8. Clinical Safety Laboratory Assessments

- See [Appendix 2](#) for the list of clinical laboratory tests to be performed and the *Schedule of activities* for the timing and frequency.
- Participants must abstain from all food and drink (except water and non-study medications) for an 8-hour overnight fast prior to labs that include the lipid profile panel on Day 1 and Week 12. All other labs do not require fasting.
- Sample collection, labeling, storage, and shipping information can be found in the laboratory manual.
- The investigator must review the laboratory report, document this review, and record any clinically relevant changes occurring during the study in the AE section of the CRF. The laboratory reports must be filed with the source documents. Clinically significant abnormal laboratory findings are those which are not associated with the underlying disease, unless judged by the investigator to be more severe than expected for the participant's condition.
- All laboratory tests with values considered clinically significantly abnormal during participation in the study or within 28 days after the last dose of study intervention should be repeated until the values return to normal or baseline or are no longer considered clinically significant by the investigator or medical monitor.
 - If such values do not return to normal/baseline within a period of time judged reasonable by the investigator, the etiology should be identified and the sponsor notified.
 - All protocol-required laboratory assessments, as defined in [Appendix 2](#), must be conducted in accordance with the laboratory manual and the [Schedule of Activities](#).
 - If laboratory values from non-protocol specified laboratory assessments performed at the institution's local laboratory require a change in participant management or are considered clinically significant by the investigator (eg, SAE or AE or dose modification), then the results must be recorded in the CRF.

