Table 7. Protocol-Required Safety Laboratory Assessments

Laboratory Assessments	Parameters
	CD8+ T cells (CD3+CD8+) NK cells (CD3-CD16+CD56+) B cells (CD3-CD19+)

1. Lipid profile panel requires at least an 8 hour fast. Lipid profile panel will be completed at Day 1 and Week 12, and will include total cholesterol, LDL, HDL, and triglycerides.
2. Microscopy performed at all visits and culture as appropriate.
3. At Screening only. HIV testing will be performed for all participants.
4. HBsAb reflex testing only if HBsAg negative but HBcAb positive. HCV RNA is reflex testing only if HCVAb is positive.
5. Participants who are HBsAg negative, HBcAb positive, and HBsAb positive will have reflex testing for HBV DNA.
6. Pregnancy testing for all WOCBP.
7. PPD results should be read within 48 to 72 hours.
- C** 9. All study-required laboratory assessments will be performed by a central laboratory, with the exception of: urine pregnancy tests, which will be performed on the Day of the study visits per the [Schedule of Activities](#).

Investigators must document their review of each laboratory safety report.

Laboratory results that could unblind the study will not be reported to investigative sites or other blinded personnel until the study has been unblinded.

10.3. Appendix 3: Adverse Events: Definitions and Procedures for Recording, Evaluating, Follow-up, and Reporting

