3.4. Baseline Variables

In general, for all analyses, baseline will be defined based on observations collected prior to first dose. Baseline values for demographics, medical and other history, atopic dermatitis history will be based on measures collected at Visit 1/Screening visit. Study Day 1 is defined as the day the subject receives first dose of study drug. For purposes of all other analyses including analyses for change from baseline, the baseline value will be defined as measured on Day 1 (before time of first dose, if time

is available). If a value is missing on Day 1, then the last available observation before Day 1 will be used.

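### As read, the protocol schedule marks the first lipid panel at Day 2, after the first dose, while four places in the text put it at Day 1; a Day 2 value cannot be the lipid baseline under the SAP

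*Protocol*

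**What the plan says.** **Schedule.** In protocol Section 1.3, as read, the lipid panel row has one mark under Day 2 (Visit 3) and one under Week 12 (Visit 10). Screening and Day 1 are empty. The row's note, "8-hour fast required", names no day.

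**Text.** Four places in the protocol give a different first time point:

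- Section 5.3.1: "On study visit days (Day 1 and Week 12), participants must comply with fasting requirements for at least 8 hours prior to the visit".
- Section 8 ties the fast to every visit with a lipid panel and names the same two visits.
- Section 8.2.8 asks for an "8-hour overnight fast prior to labs that include the lipid profile panel on Day 1 and Week 12".
- Appendix 2, Table 7, note 1: "Lipid profile panel will be completed at Day 1 and Week 12, and will include total cholesterol, LDL, HDL, and triglycerides".

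**Baseline rule.** SAP 3.4 makes Day 1 the day of first dose and takes the pre-dose Day 1 value as baseline. The only fallback is earlier: "If a value is missing on Day 1, then the last available observation before Day 1 will be used". SAP Appendix 2 closes the baseline window on the day of first dose, and its laboratory exception reaches back at most 28 days before dosing.

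**Use of the data.** Protocol 9.4.3 gives lipid profiles as an example of the safety laboratory tests. SAP 3.5.2 lists the lipid parameters, and SAP 6.8 summarises change from baseline in laboratory data.

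**The concern.** A site could reasonably work from the schedule cell. Section 8 points to the schedule for the timing of procedures and insists on adherence to it, and Section 8.2.8 sends the reader there for laboratory timing. Day 2 also looks like an attended visit: the biopsy-site examination is marked there, and only Day 8 and Day 43 are labelled as telephone contacts. A blood draw on Day 2 would not strike a coordinator as odd.

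Such a draw is post-dose. With no lipid panel marked at Screening either, there would be nothing earlier to fall back on. A missed pre-dose sample cannot be recovered later.

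**Working it through.** The plan states no figure on this point, so the check is of table positions and of the baseline rule.

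**1. Column map of the protocol schedule.** Columns 1 to 11 are Screening, Day 1, Day 2, Day 4, Day 8, Day 15, Day 29, Day 43, Day 57, Day 85 (Week 12) and Day 113; column 12 holds the notes.

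| Protocol row | Marked columns |
|---|---|
| Lipid panel | 3, 10 (note in 12) |
| Serum chemistry | 1, 2, 6, 7, 9, 10, 11 |
| Hematology | 1, 2, 4, 6, 7, 9, 10, 11 |
| Serum proteomics | 2, 6, 7, 10 |
| Biopsy-site examination | 2, 3, 4, 6, 7, 9, 10, 11 |

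The comparison rows fall on sensible visits. Serum proteomics maps to Weeks 0, 2, 4 and 12, the collection times that Section 8.8 gives for the inflammatory and cardiovascular blood markers. The grid in this part of the table therefore reads correctly in general.

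**2. Could the whole lipid row have slipped?** Moving it one column left gives columns 2 and 9, that is Day 1 and Week 8. Week 8 contradicts all four places in the text, and the note would be displaced too. Only a slip of the first mark alone would remove the conflict.

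**3. Does the SAP copy settle it?** No. In SAP Appendix 7 the lipid marks fall in columns 3 and 11, so at least the second is misplaced against Week 12.

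- If both marks slipped by one, the row reads 2 and 10: Day 1 and Week 12. The hematopoiesis row in that table behaves this way. It reads 3, 5, 7, 8, 10, 11, 12, which would put blood draws on the two telephone contacts (columns 5 and 8) and a mark in the notes column. Moved back by one it becomes 2, 4, 6, 7, 9, 10, 11.
- If only the second mark slipped, the row reads 3 and 10: Day 2 and Week 12. The SAP weight row behaves this way, at 1 and 11 against 1 and 10 in the protocol.

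**4. The baseline rule applied to each reading.**

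| First lipid draw | Before first dose? | SAP Appendix 2 window | Scheduled pre-dose lipid samples | Week 12 change from scheduled samples |
|---|---|---|---|---|
| Day 1, pre-dose | Yes | Baseline | 1 | Computable |
| Day 2 | No | Week 2 (Days 2 to 22) | 0 (Screening 0 + Day 1 0) | Not computable |

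The later sample, Day 85, falls in the Week 12 window (Days 72 to 99) under either reading. The Week 2 label for a Day 2 value applies only if these windows are used, since SAP Appendix 2 lets safety analyses follow the sponsor's reporting standards instead.

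**The case against.** The strongest objection is that this is a reading artefact. The Day 2 position rests on one cell of a table extracted from PDF, and single cells do slip in these documents. In SAP Appendix 7 the drug dispensing row reads columns 2, 8, 9, while the protocol has 2, 7, 9 and SAP 6.7.3 confirms dispensing at Weeks 0, 4 and 8. One mark moved one column right while its neighbours stayed put, which is the slip that would turn Day 1 into Day 2. This stands: it cannot be excluded without the source PDF, and if the cell sits under Day 1 there, the point falls away.

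The second objection is that the text is explicit and consistent. Section 8, which refers sites to the schedule, itself names Day 1, and Day 1 chemistry is drawn anyway. This also stands, and it limits the likely harm.

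A third objection is that SAP 3.5.2 lists lipids within clinical chemistry, which is drawn at Screening and Day 1. This does not supply a baseline, because Table 7 and the schedule keep the lipid panel as a separate test.

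A reader might also infer that a Day 2 draw would be unfasted. The documents do not support that. The row's own note asks for a fast, Section 8 asks for one before every visit with a lipid panel, and Table 7 note 1 requires one for the panel itself.

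**Conclusion.** On the text supplied, the schedule row and four places in the protocol disagree on when the first lipid sample is taken. The choice decides whether a scheduled lipid baseline exists: 0 scheduled pre-dose samples per participant if the schedule cell is followed, 1 if the text is followed with a pre-dose draw.

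It would be tempting to say that all of the approximately 51 participants lose their lipid baseline, or that sites must at least be split. Neither follows. The documents do not show which instruction sites used, so the number affected could lie anywhere from none to all. An unscheduled pre-dose lipid result would still qualify under SAP 3.4. Nor can the SAP schedule be called wrong on this row, because its columns have slipped.

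The consequence is confined to descriptive summaries of lipid change from baseline. The primary biomarker endpoints are untouched, and no discontinuation criterion in protocol Appendix 10 uses lipids. The conclusion assumes that the extracted cell matches the source table, so confidence is moderate. The point merits correction because the repair is small and lost baseline samples cannot be recovered.

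**What to change.** 1. Check the first mark of the lipid panel row in protocol Section 1.3 against the source PDF. If it sits under Day 1, nothing further is needed for the protocol.
2. If it sits under Day 2, reconcile the row with Sections 5.3.1, 8 and 8.2.8 and Table 7 note 1, and state in the row's note that the first sample is fasting and pre-dose. For the analysis, what matters is that a pre-dose fasting sample exists, since only that can be the baseline under SAP 3.4.
3. Check the lipid row of SAP Appendix 7 against its own source and align it with the protocol.
4. If any participants have already had their first lipid sample on Day 2, report how many lack a pre-dose value and show the Day 2 value as post-dose, not as baseline.

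The cost is about one cell in each schedule table plus a few words in the note. If the first sample is taken at the Day 1 visit, no extra venepuncture is needed, because chemistry and hematology are already drawn then.

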2. INTRODUCTION

Abrocitinib is a Janus kinase 1 (JAK1) inhibitor that is being investigated as a treatment for patients with moderate-to-severe AD.

The Janus kinase (JAK) family, including JAK1, JAK2, JAK3, and tyrosine kinase 2 (TYK2), is a group of cytoplasmic tyrosine kinases that mediate signal transduction via interactions with Type 1 and Type 2 cytokine receptors critical for leukocyte activation, proliferation, survival, and function. Cytokine receptors demonstrate restricted association with JAKs such that different receptors or receptor classes preferentially utilize a given JAK dimer combination to transduce their signal. JAK1 pairs with JAK3 to mediate γ -common cytokine signaling and also with JAK2 or TYK2 to transmit the signals of additional cytokines important in inflammation and immune responses, including interleukin (IL)-4, IL-5, IL-6, IL-13, IL-21, IL-31, interferon-gamma (IFN- γ), and IFN-alpha (IFN- α). JAK2 homodimers are critical for the signaling of hematopoietic cytokines and hormones, including thrombopoietin (TPO), erythropoietin (EPO), IL-3, granulocyte-macrophage colony-stimulating factor, and prolactin. IL-12, EPO, and IL-23 are dependent on TYK2 and JAK2 for transmitting their signals.

Following cytokine activation, receptor-associated JAKs are phosphorylated and in turn phosphorylate specific sites on the receptor intracellular domain. Phosphorylation of specific sites on the intracellular domain of the receptor allows for the recruitment of signal transducers and activators of transcription (STATs) that can subsequently be phosphorylated by JAKs. Phosphorylated STAT molecules are released from the receptor, translocate to the nucleus where they bind to specific sites on deoxyribonucleic acid (DNA), and regulate gene transcription.

The inflammatory skin disorder AD is characterized by epidermal barrier dysfunction and active AD lesions are accompanied by underlying immune activation.^{1,2,3} Skin lesions have shown increased infiltration by T cells, dendritic cells (DCs), and eosinophils; increased production of cytokines and chemokines; and reactive epidermal hyperplasia, in which epidermal differentiation products (ie, filaggrin and loricrin) are highly suppressed.^{4,5,6} Although AD has been classified as a Th2-dominated disease, other T-cell subsets (eg, Th22, Th17, and Th1 cells) might also contribute to pathogenesis.^{2,3} Key cytokines implicated in the pathophysiology of AD include IL-4, IL-5, IL-13, IL-31, and IFN- γ . These cytokines require JAK1 for signal transduction suggesting that selective JAK1 inhibitors, which modulate the activity of these cytokines, represent a compelling approach to the treatment of inflammatory skin diseases such as AD.⁷

Data from a Phase 2b proof of concept (POC) study (B7451006) that evaluated participants with moderate-to-severe AD showed positive efficacy with the JAK1 inhibitor abrocitinib, as well as an acceptable safety profile, sufficient to support further clinical development in a larger Phase 3 program. Abrocitinib is an orally bioavailable small molecule that selectively inhibits JAK1 by blocking the adenosine triphosphate (ATP) binding site. Abrocitinib has a high degree of selectivity in vitro against other kinases: 28-fold selectivity over JAK2, >340-fold over JAK3 and 43-fold over TYK2, as well as a good selectivity profile over the broader range of human kinases.

Abrocitinib Involvement in Hematopoiesis

In Study B7451006 there were dose-dependent decreases in mean platelet counts in the abrocitinib 200 mg once daily (QD) and 100 mg QD doses with a nadir at Week 4 (200 mg QD: -29.84%; 100 mg QD: -11.42%). Platelet counts resolved on treatment and returned to baseline by 4 weeks after end of treatment. The majority of participants maintained platelet counts within the normal range. No participant had an AE related to sequelae from thrombocytopenia (ie, bleeding or bruising). In addition, changes in total reticulocytes (absolute) were observed in all treatment groups, but were generally not clinically relevant. The abrocitinib 200 mg QD group had the greatest mean percent change from baseline in reticulocytes, for which decreases from baseline were observed during Week 1 to Week 6 with a maximal decrease at Week 2, and increases from baseline were observed during Week 8 to Week 16.

The human body produces and removes 10^{11} platelets daily to maintain a normal steady-state platelet count. Platelet production must be tightly regulated to avoid spontaneous bleeding or arterial occlusion and organ damage. Multifaceted and complex mechanisms control platelet removal and production in physiological and pathological conditions. Production of red blood cells (RBCs) is a highly regulated process; however, the time of RBCs in circulation is longer (approximately 120 days) than that of platelets (8-9 days). Reticulocytes (immature RBCs that mature to RBCs in 2-3 days) have a shorter time, and as such, may be a more sensitive indicator of JAK inhibition on RBC production. Both platelets and RBC derive from the same progenitor. Hence, changes in one compartment can affect the other.

The Ashwell-Morrell receptor (AMR) recognizes senescent, desialylated platelets under steady-state conditions.⁸ Desialylated platelets and the AMR are the physiological ligand-receptor pair regulating hepatic TPO messenger ribonucleic acid (mRNA) production, resolving the longstanding question of steady-state TPO regulation. The AMR-mediated removal of desialylated platelets regulates TPO synthesis in the liver by recruiting JAK2 and STAT3 to increase thrombopoiesis. Inhibition of TPO production downstream of the hepatic AMR-JAK2 signaling cascade could additionally contribute to thrombocytopenia associated with JAK1/2 treatment.

2.1. Study Rationale

Abrocitinib is being developed as an oral treatment for patients with moderate-to-severe AD based on the clinical results obtained in Phase 1 and Phase 2 studies. Additional information for the Phase 1 and Phase 2 study results previously completed may be found in the Investigator's Brochure (IB). Phase 3 studies are ongoing to evaluate abrocitinib as monotherapy or when co-administered with background medicated topical therapy in adults or adolescents with AD.

This study (B7451037) is designed specifically to evaluate abrocitinib monotherapy in adults with AD to characterize the mechanism of action of abrocitinib and assess the effects of abrocitinib on the molecular signature of JAK1 inhibition in lesional and non-lesional skin and its correlation to clinical efficacy outcomes. The JAK1 AD Study B7451006 showed dose-dependent, self-limited decrease in platelet counts, but did not provide any mechanistic

insights. 

